7.1.3 Interaction with other medications

Cabozantinib

Aprepitant: May increase the serum concentration of CYP3A4 Substrates (High risk with Inhibitors). Risk C: Monitor therapy

Bisphosphonate Derivatives: Angiogenesis Inhibitors (Systemic) may enhance the adverse/toxic effect of Bisphosphonate Derivatives. Specifically, the risk for osteonecrosis of the jaw may be increased. Risk C: Monitor therapy

Bosentan: May decrease the serum concentration of CYP3A4 Substrates (High risk with Inducers). Risk C: Monitor therapy

Clofazimine: May increase the serum concentration of CYP3A4 Substrates (High risk with Inhibitors). Risk C: Monitor therapy

Conivaptan: May increase the serum concentration of CYP3A4 Substrates (High risk with Inhibitors). Risk X: Avoid combination

CYP3A4 Inducers (Moderate): May decrease the serum concentration of CYP3A4 Substrates (High risk with Inducers). Risk C: Monitor therapy

CYP3A4 Inducers (Strong): May decrease the serum concentration of Cabozantinib. Management: Avoid use of strong CYP3A4 inducers with cabozantinib if possible. If combined, cabozantinib dose adjustments are recommended and vary based on the cabozantinib product used and the indication for use. See monograph for details. Risk D: Consider therapy modification

CYP3A4 Inhibitors (Moderate): May decrease the metabolism of CYP3A4 Substrates (High risk with Inhibitors). Risk C: Monitor therapy

CYP3A4 Inhibitors (Strong): May increase the serum concentration of Cabozantinib. Management: Avoid use of a strong CYP3A4 inhibitor with cabozantinib if possible. If combined, cabozantinib dose adjustments are recommended and vary based on the cabozantinib product used and the indication for use. See monograph for details. Risk D: Consider therapy modification

Dabrafenib: May decrease the serum concentration of CYP3A4 Substrates (High risk with Inducers). Management: Seek alternatives to the CYP3A4 substrate when possible. If concomitant therapy cannot be avoided, monitor clinical effects of the substrate closely (particularly therapeutic effects). Risk D: Consider therapy modification

Duvelisib: May increase the serum concentration of CYP3A4 Substrates (High risk with Inhibitors). Risk C: Monitor therapy

Enzalutamide: May decrease the serum concentration of CYP3A4 Substrates (High risk with Inducers). Management: Concurrent use of enzalutamide with CYP3A4 substrates that have a narrow therapeutic index should be avoided. Use of enzalutamide and any other CYP3A4 substrate should be performed with caution and close monitoring. Risk D: Consider therapy modification

Erdafitinib: May decrease the serum concentration of CYP3A4 Substrates (High risk with Inducers). Risk C: Monitor therapy

Erdafitinib: May increase the serum concentration of CYP3A4 Substrates (High risk with Inhibitors). Risk C: Monitor therapy

Fosaprepitant: May increase the serum concentration of CYP3A4 Substrates (High risk with Inhibitors). Risk C: Monitor therapy

Fosnetupitant: May increase the serum concentration of CYP3A4 Substrates (High risk with Inhibitors). Risk C: Monitor therapy

Fusidic Acid (Systemic): May increase the serum concentration of CYP3A4 Substrates (High risk with Inhibitors). Risk X: Avoid combination

Grapefruit Juice: May increase the serum concentration of Cabozantinib. Risk X: Avoid combination

Idelalisib: May increase the serum concentration of CYP3A4 Substrates (High risk with Inhibitors). Risk X: Avoid combination

Ivosidenib: May decrease the serum concentration of CYP3A4 Substrates (High risk with Inducers). Risk C: Monitor therapy

Larotrectinib: May increase the serum concentration of CYP3A4 Substrates (High risk with Inhibitors). Risk C: Monitor therapy

Lorlatinib: May decrease the serum concentration of CYP3A4 Substrates (High risk with Inducers). Management: Avoid concurrent use of Iorlatinib with any CYP3A4 substrates for which a minimal decrease in serum concentrations of the CYP3A4 substrate could lead to therapeutic failure and serious clinical consequences. Risk D: Consider therapy modification

MiFEPRIStone: May increase the serum concentration of CYP3A4 Substrates (High risk with Inhibitors). Management: Minimize doses of CYP3A4 substrates, and monitor for increased concentrations/toxicity, during and 2 weeks following treatment with mifepristone. Avoid cyclosporine, dihydroergotamine, ergotamine, fentanyl, pimozide, quinidine, sirolimus, and tacrolimus. Risk D: Consider therapy modification

Mitotane: May decrease the serum concentration of CYP3A4 Substrates (High risk with Inducers). Management: Doses of CYP3A4 substrates may need to be adjusted substantially when used in patients being treated with mitotane. Risk D: Consider therapy modification

MRP2 Inhibitors: May increase the serum concentration of Cabozantinib. Risk C: Monitor therapy

Netupitant: May increase the serum concentration of CYP3A4 Substrates (High risk with Inhibitors). Risk C: Monitor therapy

Palbociclib: May increase the serum concentration of CYP3A4 Substrates (High risk with Inhibitors). Risk C: Monitor therapy

Pitolisant: May decrease the serum concentration of CYP3A4 Substrates (High risk with Inducers). Management: Combined use of pitolisant with a CYP3A4 substrate that has a narrow therapeutic index should be avoided. Other CYP3A4 substrates should be monitored more closely when used with pitolisant. Risk D: Consider therapy modification

Protocol #: UCI 18-124 MP 10/11//2022

Rifabutin: May decrease the serum concentration of Cabozantinib. Risk C: Monitor therapy

Rifapentine: May decrease the serum concentration of Cabozantinib. Risk C: Monitor therapy

Sarilumab: May decrease the serum concentration of CYP3A4 Substrates (High risk with Inducers). Risk C: Monitor therapy

Siltuximab: May decrease the serum concentration of CYP3A4 Substrates (High risk with Inducers). Risk C: Monitor therapy

Simeprevir: May increase the serum concentration of CYP3A4 Substrates (High risk with Inhibitors). Risk C: Monitor therapy

St John's Wort: May decrease the serum concentration of Cabozantinib. Risk X: Avoid combination

Stiripentol: May increase the serum concentration of CYP3A4 Substrates (High risk with Inhibitors). Management: Use of stiripentol with CYP3A4 substrates that are considered to have a narrow therapeutic index should be avoided due to the increased risk for adverse effects and toxicity. Any CYP3A4 substrate used with stiripentol requires closer monitoring. Risk D: Consider therapy modification

Tocilizumab: May decrease the serum concentration of CYP3A4 Substrates (High risk with Inducers). Risk C: Monitor therapy

Pembrolizumab

Thalidomide Analogues: Pembrolizumab may enhance the adverse/toxic effect of Thalidomide Analogues. Specifically, mortality may be increased when this combination is used for treatment of refractory multiple myeloma. Risk X: Avoid combination.

7.1.4 Adverse Reactions

Cabozantinib

>10%:

Cardiovascular: Hypertension (30% to 61%)

Central nervous system: Fatigue (41% to 56%), mouth pain (36%), voice disorder (19%), headache (11% to 18%), dizziness (11% to 14%)

Dermatologic: Palmar-plantar erythrodysesthesia (42% to 50%), hair discoloration (34%), skin rash (19% to 23%), xeroderma (11% to 19%), alopecia (16%), erythema (11%)

Endocrine & metabolic: Increased lactate dehydrogenase (84%), increased serum triglycerides (53%), hypocalcemia (8% to 52%), hypoalbuminemia (36% to 51%), hypophosphatemia (25% to 48%), weight loss (17% to 48%), hyperglycemia (37%), hypomagnesemia (19%)

CONFIDENTIAL

to 31%), hyponatremia (10% to 30%), increased gamma-glutamyl transferase (27%), hypokalemia (18% to 23%), hypothyroidism (8% to 21%)

Gastrointestinal: Diarrhea (54% to 74%), stomatitis (13% to 51%; grades 3/4: 2% to 5%), nausea (31% to 50%), decreased appetite (46% to 48%), dysgeusia (12% to 34%), vomiting (24% to 32%), constipation (25% to 27%), abdominal pain (23% to 27%), mucositis (14% to 19%), increased serum amylase (16%), dysphagia (13%), dyspepsia (10% to 12%)

Genitourinary: Proteinuria (2% to 12%)

Hematologic & oncologic: Lymphocytopenia (25% to 53%; grades 3/4: 1% to 16%), neutropenia (31% to 43%; 35%; grades 3/4: 2% to 7%), leukopenia (35%), thrombocytopenia (25% to 35%; grades 3/4: 1%), anemia (17% to 31%; grades 3/4: 1% to 5%)

Hepatic: Increased serum aspartate aminotransferase (73% to 86%), increased serum alanine aminotransferase (68% to 86%), increased serum alkaline phosphatase (35% to 52%), hyperbilirubinemia (25%)

Neuromuscular & skeletal: Asthenia (19% to 22%), arthralgia (11% to 14%), limb pain (9% to 14%), muscle spasm (8% to 13%)

Renal: Increased serum creatinine (58%)

Respiratory: Dyspnea (12% to 19%), cough (18%)

1% to 10%:

Cardiovascular: Hypotension (7%), venous thromboembolism (6% to 7%), syncope (grades 3/4: 5%), pulmonary embolism (4%), arterial thromboembolism (1% to 2%), vascular disease (grades 3/4: 1%)

Central nervous system: Anxiety (9%), paresthesia (7%), peripheral sensory neuropathy (7%), pain (grades 3/4: 5%), peripheral neuropathy (5%), depression (grades 3/4: 4%), confusion (grades 3/4: 1%)

Dermatologic: Hyperkeratosis (7%), dermal ulcer (grades 3/4: 3%)

Endocrine & metabolic: Dehydration (7%), hyperkalemia (grades 3/4: 1%)

Gastrointestinal: Hemorrhoids (9%), gastrointestinal hemorrhage (3%), gastrointestinal perforation (1% to 3%), gastrointestinal fistula (1%)

Hematologic & oncologic: Increased hemoglobin (8%), hemorrhage (grade ≥3: 5%)

Neuromuscular & skeletal: Musculoskeletal chest pain (9%), back pain (grades 3/4: 4%), ostealgia (grades 3/4: 3%), osteonecrosis of the jaw (≤1%)

Renal: Acute renal failure (grades 3/4: 4%)

Respiratory: Pulmonary infection (grades 3/4: 4%)

Miscellaneous: Fistula (nongastrointestinal: 4%; includes tracheal/esophageal), wound healing impairment (≤2%)

<1%, postmarketing, and/or case reports: Cholestatic hepatitis, hypertensive crisis, nephrotic syndrome, pancreatitis, reversible posterior leukoencephalopathy syndrome, seizure

Pembrolizumab

>10%:

Cardiovascular: Peripheral edema (14% to 15%), cardiac arrhythmia (11%)

Central nervous system: Fatigue (23% to 43%), pain (22%), headache (11% to 14%)

Dermatologic: Pruritus (11% to 28%), skin rash (13% to 24%), vitiligo (13%)

Endocrine & metabolic: Hyperglycemia (19% to 49%), hypoalbuminemia (27% to 44%), hypertriglyceridemia (33% to 43%), hyponatremia (10% to 38%), hypophosphatemia (19% to 29%), hypocalcemia (15% to 27%), decreased serum bicarbonate (22%), hypercholesterolemia (20%), hypokalemia (15% to 20%), hypoglycemia (13% to 19%), hypothyroidism (9% to 15%), hypercalcemia (14%), hyperkalemia (13%), weight loss (10% to 11%)

Gastrointestinal: Diarrhea (13% to 28%), decreased appetite (16% to 25%), constipation (14% to 22%), abdominal pain (13% to 22%), nausea (11% to 22%), vomiting (12% to 19%)

Genitourinary: Urinary tract infection (15% to 19%), hematuria (12% to 13%)

Hematologic & oncologic: Anemia (17% to 54%; grades 3/4: 4% to 24%), lymphocytopenia (24% to 47%; grades 3/4: 1% to 18%), leukopenia (35%; grades 3/4: 9%), neutropenia (24% to 30%; grades 3/4: 7% to 11%), thrombocytopenia (27%; grades 3/4: 4%), hemorrhage (19%; grades 3/4: 5%), increased INR (19%), prolonged partial thromboplastin time (14%)

Hepatic: Increased serum alkaline phosphatase (17% to 42%), increased serum transaminases (27% to 34%), increased serum aspartate aminotransferase (20% to 34%), increased serum alanine aminotransferase (9% to 27%), increased liver enzymes (13%)

Protocol #: UCI 18-124 MP 10/11//2022

Immunologic: Graft versus host disease (followed by allogeneic hematopoietic stem cell transplantation: 26%)

Infection: Infection (16%)

Neuromuscular & skeletal: Musculoskeletal pain (21% to 32%), arthralgia (10% to 18%), back pain (11% to 12%), asthenia (10% to 11%)

Renal: Increased serum creatinine (11% to 35%)

Respiratory: Upper respiratory tract infection (13% to 28%), cough (14% to 26%), dyspnea (10% to 23%), flu-like symptoms (11%)

Miscellaneous: Fever (11% to 28%)

1% to 10%:

Cardiovascular: Facial edema (10%), pericarditis (4%), pericardial effusion (2%)

Central nervous system: Peripheral neuropathy (2% to 10%)

Endocrine & metabolic: Hyperthyroidism (3% to 10%), thyroiditis (≤2%)

Gastrointestinal: Colitis (2%)

Hepatic: Hyperbilirubinemia (10%), hepatic sinusoidal obstruction syndrome (followed by allogeneic hematopoietic stem cell transplantation: 9%), ascites (grades 3/4: 8%), hepatitis (≤3%)

Immunologic: Antibody development (2%; neutralizing: <1%)

Neuromuscular & skeletal: Arthritis (2%), myositis (≤1%)

Ophthalmic: Uveitis (≤1%)

Renal: Acute renal failure (2%)

Respiratory: Pneumonitis (2% to 3%)

Miscellaneous: Infusion-related reaction (≤9%)

Frequency not defined:

Cardiovascular: Cardiac failure, cardiac tamponade, edema, myocardial infarction, septic shock

Central nervous system: Confusion, polyneuropathy

Dermatologic: Maculopapular rash

Infection: Herpes zoster

Respiratory: Pleural effusion, pneumonia, respiratory failure

CONFIDENTIAL

Miscellaneous: Fistula, physical health deterioration

<1%, postmarketing, and/or case reports: Anaphylaxis, chronic inflammatory demyelinating polyradiculoneuropathy (Maleissye 2016), diabetic ketoacidosis, encephalitis, Guillain-Barré syndrome, hemolytic anemia, hypersensitivity reaction, hypophysitis, myasthenia gravis, myelitis, myocarditis, nephritis, organ transplant rejection (solid), pancreatitis, sarcoidosis, type 1 diabetes mellitus, vasculitis

7.2 Adverse Event Monitoring

Adverse event data collection and reporting, which are required as part of every clinical trial, are done to ensure the safety of Subjects enrolled in the studies as well as those who will enroll in future studies using similar agents. Adverse events are reported in a routine manner at scheduled times during a trial. Additionally, certain adverse events must be reported in an expedited manner to allow for optimal monitoring of patient safety and care.

All patients experiencing an adverse event, regardless of its relationship to study drug, will be monitored until:

- the adverse event resolves or the symptoms or signs that constitute the adverse event return to baseline;
- any abnormal laboratory values have returned to baseline;
- there is a satisfactory explanation other than the study drug for the changes observed; or
- > death.

7.3 Definitions

7.3.1 Event Definitions

Adverse event (AE) - An adverse event is any untoward medical experience or change of an existing condition that occurs during or after treatment, whether or not it is considered to be related to the protocol intervention.

Unexpected Adverse Event [Modified from the definition of unexpected adverse drug experience in FDA regulations at 21 CFR 312.32 (a)] – An adverse event is unexpected if it is not listed in the investigator's brochure and/or package insert; is not listed at the specificity or severity that has been observed; is not consistent with the risk information described in the protocol and/or consent; is not an expected natural progression of any underlying disease, disorder, condition, or predisposed risk factor of the research participant experiencing the adverse event.

Expected Adverse Event - Any event that does not meet the criteria for an unexpected event OR is an expected natural progression of any underlying disease, disorder, condition, or predisposed risk factor of the research participant experiencing the adverse event.

Serious Adverse Event (SAE) [21 CFR 312.32] - defined as *any expected or unexpected adverse event* that result in any of the following outcomes:

Death

- Is life-threatening experiences (places the subject at immediate risk of death from the event as it occurred)
- Unplanned hospitalization equal or greater than 24 hours)) or prolongation of existing hospitalization
- · A persistent or significant disability/incapacity
- A congenital anomaly/birth defect
- Any other adverse event that, based upon appropriate medical judgment, may jeopardize the subject's health and may require medical or surgical intervention to prevent one of the outcomes listed above (examples of such events include allergic bronchospasm requiring intensive treatment in the emergency room or at home, blood dyscrasias of convulsions that do not result in inpatient hospitalization, or the development of drug dependency or drug abuse).

Unanticipated problem (UP) - Any incident, experience or outcome that meets **all three** of the following criteria:

- Unexpected (in term nature, severity, or frequency) given the following:

 a) the research procedures described in the protocol-related documents such as the IRB approved research protocol, informed consent document or Investigator Brochure (IB); and b) the characteristics of the subject population being studied; AND
- Related or possibly related to participation in the research (possibly related means there is a reasonable possibility that the incident, experience, or outcomes may have been caused by the drugs, devices or procedures involved in the research); AND
- Suggests that the research places subjects or others at greater risk of harm (including physical, psychological, economic, or social harm) than previously known or recognized.

Protocol Violation- A protocol violation is an accidental or unintentional change to or noncompliance with the IRB-approved protocol that increases risk or decreases benefit and/or affects the subject's rights, safety, welfare, and/or the integrity of the data. Examples of incidents that may be considered violations include: enrolling a participant who does not meet the inclusion criteria; obtaining verbal consent before the initiation of study procedures when the IRB requires signed, written informed consent; and failure to collect screening labs before initiation of study procedures [Reference: Policy #57 UCI HRPP Policy and Procedure Glossary].

Protocol Deviation- a protocol deviation is an accidental or unintentional change to the research protocol that does not increase risk or decrease benefit or have a significant effect on the participant's rights, safety or welfare, or on the integrity of the data. Deviations may result from the action of the participant, researcher, or staff. Examples: a rescheduled study visit, an omitted routine safety lab for a participant with previously normal values; or failure to collect an ancillary self-report questionnaire data (e.g., quality of life) [Reference: Policy #57 UCI HRPP Policy and Procedure Glossary].

7.3.2 Characteristics and Severity of Adverse Events

All non-hematologic adverse events will be graded according to the NCI Common Terminology Criteria for Adverse Events (CTCAE) version 5.0. The CTCAE v5 is available at:

https://ctep.cancer.gov/protocoldevelopment/electronic_applications/ctc.htm#ctc_50

If no CTCAE grading is available, the severity of an AE is graded as follows:

Mild (grade 1): the event causes discomfort without disruption of normal daily activities.

Moderate (grade 2): the event causes discomfort that affects normal daily activities.

Severe (grade 3): the event makes the patient unable to perform normal daily activities or significantly affects his/her clinical status.

Life-threatening (grade 4): the patient was at risk of death at the time of the event.

Fatal (grade 5): the event caused death.

- Expectedness": AEs can be 'Unexpected' or 'Expected'
 - **-Unexpected:** (in terms of nature, severity, or frequency) given (a) the research procedures that are described in the IRB-approved documents, such as the protocol and informed consent document; and (b) the characteristics of the subject population being studied;
- Attribution of the AE:
- *Related The AE is clearly related to the study treatment.*
- *Not Related The AE is clearly NOT related to the study treatment.*

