2.3 Endpoints

The primary endpoint is 6 months progression-free survival (PFS-6). The secondary endpoints are rates of drug-related grade 3-5 adverse events experienced during and up to four weeks after completion of study treatment. These will be assessed via NCI's CTCAE v5.0 toxicity criteria. Other secondary endpoints are best objective response rate by RECIST v1.1 in patients with measurable disease and overall survival.

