4.2 Toxicities and Dosing Delays/Dose Modifications

Any patient who receives treatment on this protocol will be evaluable for toxicity. Each patient will be assessed for the development of toxicity according to the Time and Events table (Section 5.5). Toxicity will be assessed according to the NCI Common Toxicity Criteria for Adverse Events (CTCAE), version 5.0. Dose adjustments should be made according to the system showing the greatest degree of toxicity.

Cabozantinib and pembrolizumab have class specific safety profiles based on their mechanism of action but may also cause AEs that overlap. For management of AEs which can be clearly attributed to cabozantinib or pembrolizumab, independent dose modification for either agent is allowed. Examples of VEGFR TKI associated AEs caused by cabozantinib are hypertension and hand-foot syndrome. Examples of immune-related AEs caused by pembrolizumab are pneumonitis and endocrinopathies. For AEs without clear attribution to either study treatment, management of toxicity should include dose modifications of both agents per the discretion of the investigator. Examples of overlapping AEs are diarrhea and transaminase increases.

Protocol #: UCI 18-124 MP 10/11//2022

Dose Modification Table

Dose Level	Agent	Dose
1 (starting dose)	Cabozantinib	40 mg
1 (starting dose)	Pembrolizumab	200 mg
-1 (50% reduction)	Cabozantinib	20 mg
-2	Cabozantinib	20 mg every other day

Toxicities:

Toxicity Dose Reductions			
NCI CTC Grade	Cabozantinib	Pembrolizumab	
Grade 0-2	No change from original starting dose	No change from original starting dose (unless described in 4.2.1)	
Intolerable grade 2 or grade 3	Hold until resolved to < Grade 1 then resume to dose level 1 or -1, depending on physician assessment	Hold until resolved to < Grade 2, then resume at dose level 1 (unless described in 4.2.1)	
Second episode of grade 3 or intolerable grade 2 first episode of grade 4 toxicity	Hold until resolved to ≤ Grade 1 then reduce to dose level one less than previous (i.e1 or -2) Discontinue permanently (unless investigator determines patient is deriving clear clinical benefit)	Discontinue permanently (unless described in 4.2.1)	
Third episode of grade 3	Remove subject from trial	Not applicable	

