6.2 Safety/tolerability

Analyses will be performed for all patients having received at least one dose of study drug. The study will use the CTCAE version 5.0 for reporting of non-hematologic adverse events (http://ctep.cancer.gov/reporting/ctc.html) and modified criteria for hematologic adverse events.

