7.5 Additional Reporting of Events to the CFCCC DSMB and Sponsor Investigator

Adverse Event/ Serious Adverse Events

Event Type	Reporting Timeframe to CFCCC DMSB (Notification is done by entering this information into OnCore within the timelines below)	Reporting Timeframe to Coordinating Center (Notification is done via email to [contact] and [contact] within the timelines below)
Serious Adverse Events (all attributions) that meet all of the following criteria: Unexpected Grades 3-5 Occurring during treatment or within 30 days of the end of treatment*	5 business days from date the PI is aware of the event	24 hours from date the site is aware of the event.
Adverse Events that meet all of the following criteria: Unexpected Study related (possibly, probably, or definitely) Grades 3-4 Occurring during treatment or within 30 days of the end of treatment*	5 business days from date the PI is aware of the event	24 hours from date the site is aware of the event.
All other Adverse Events and Serious Adverse Events should be reported as noted in the 'Recording of Events' section * Investigators are not obligated to actively seek information regarding the occurrence of recording to the accurrence of recording the	Prior to each scheduled progress review.	5 business days from the date the site is aware of the event

^{*} Investigators are not obligated to actively seek information regarding the occurrence of new AEs or SAEs beginning after the 30-day post-treatment period. However, if the investigator learns of such an event and that event is deemed relevant to the study, he/she should promptly document and report the event.

Deviations/Violations

Event Type	Reporting Timeframe to CFCCC DSMB (Notification is done by entering this information into OnCore within the timelines below)	Reporting Timeframe to Coordinating Center (Or other entity monitoring/coordinating the trial)
Violations as defined above (e.g. wrong dosage of drug administered, safety procedures not being conducted at specific time points).	5 business days from the date the PI is aware of the event	24 hours from the date the site is aware of the event

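### The drug-related grade 3-5 safety endpoint is governed by conflicting attribution and grading rules, so its rate is not reproducible

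*Combined protocol and SAP*

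**What the plan says.** The endpoint is set in section 2.3: "The secondary endpoints are rates of drug-related grade 3-5 adverse events experienced during and up to four weeks after completion of study treatment". The same section names the grading standard without exception: "These will be assessed via NCI's CTCAE v5.0 toxicity criteria". Section 9.1 lists safety as a secondary endpoint and refers back to section 7 for its content. Section 9.3 adds no counting rule.

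**Attribution.** Section 7.3.2 is the only place that defines attribution categories for adverse events. It has two. Related is defined as "The AE is clearly related to the study treatment", and Not Related is its mirror image, requiring that the event clearly has nothing to do with treatment. Section 7.5 makes one of its expedited reporting rows depend on a different scale: "Study related (possibly, probably, or definitely". In section 7.3.1, the definition of an unanticipated problem also accepts a possible relation and explains it as a reasonable possibility of causation.

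**Grading.** Section 4.2 agrees with 2.3: "Toxicity will be assessed according to the NCI Common Toxicity Criteria for Adverse Events (CTCAE), version 5.0". Section 6.2 keeps CTCAE v5.0 for non-hematologic events but uses "modified criteria for hematologic adverse events". Section 7.3.2 has the same restriction: "All non-hematologic adverse events will be graded according to the NCI Common Terminology Criteria for Adverse Events (CTCAE) version 5.0". The modified criteria are neither defined nor referenced anywhere in the document.

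**The concern.** An endpoint that counts drug-related events needs a rule that places every event on one side or the other. Here an event of uncertain cause has no category under 7.3.2, yet it would count as related under the wording of 7.5. Section 2.3 does not say which wording defines drug-related.

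The trial has one arm, so no control rate is available to correct for attribution: the definition settles the number. Events of this grade also occur without the drug. The placebo-controlled hepatocellular carcinoma trial summarized in section 1.2 had grade 3 or 4 events in 36% of placebo patients and 68% of cabozantinib patients. That trial differs in disease, dose and regimen, and the figures do not measure how often attribution was uncertain. They show only that a substantial background exists.

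Two things are at stake: whether two analysts with the same records would report the same drug-related rate, and whether the expedited reporting row in 7.5 can be applied from what 7.3.2 tells the investigator to record.

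**Working it through.** The plan gives no expected rate, precision or test for this endpoint, so there is no stated figure to reproduce. The check sets the rules side by side and then works out how far they can move the result.

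**1. Attribution rules applied to the same event**

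- Definitely due to treatment: Related under 7.3.2; related under 7.5.
- Definitely not due to treatment: Not Related under 7.3.2; not related under 7.5.
- Possibly or probably due to treatment: no category under 7.3.2; related under 7.5.

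The two scales agree at the ends and differ only for the uncertain group. For that group 7.3.2 is silent rather than wrong in a known direction: the event fails both definitions.

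**2. Size of the attribution gap**

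Let N be the number of patients, c the number with at least one clearly related grade 3-5 event, and u the number whose only candidate events are uncertain.

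- Strict reading (count only clearly related): c/N.
- Inclusive reading (count everything not clearly unrelated): (c + u)/N.
- Gap: u/N. Each such patient contributes 1/27 = 3.7 points at the full 27, or 1/19 = 5.3 points if the trial ends at 19.

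The documents give neither c nor u. As an assumed example with N = 27, c = 8 and u = 6:

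- Strict: 8/27 = 29.6% (exact 95% interval 13.8% to 50.2%).
- Inclusive: 14/27 = 51.9% (31.9% to 71.3%).
- Gap: 6/27 = 22.2 points. With u anywhere from 1 to 6 the gap runs from 3.7 to 22.2 points.

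If k of the six are truly drug-related, the strict count is too low by k and the inclusive count too high by 6 − k. At k = 6 only the strict count is wrong; at k = 0 only the inclusive count is.

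**3. Grading rules**

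- Sections 2.3 and 4.2: CTCAE v5.0 for all events.
- Sections 6.2 and 7.3.2: CTCAE v5.0 for non-hematologic events only, with an unspecified modification for the others.

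The fallback severity scale in 7.3.2 does not fill the gap. It applies where CTCAE has no grading, and it is worded around discomfort, daily activities and clinical status, with no laboratory thresholds.

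Hematologic events are common enough to matter. Section 7.1.4 lists grade 3/4 anemia in 4% to 24% of patients on pembrolizumab, which is 27 × 0.04 = 1.1 to 27 × 0.24 = 6.5 patients. It also lists grade 3/4 lymphocytopenia in 1% to 18% on pembrolizumab and 1% to 16% on cabozantinib. Whether the modification would raise or lower these grades cannot be determined.

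Two attribution readings and two grading readings give four possible numerators from the same records.

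**4. Expedited reporting**

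In 7.5, unexpected serious events of grade 3-5 are expedited whatever their attribution, so they are unaffected. The row that depends on attribution covers unexpected grade 3-4 adverse events, which in practice means the non-serious ones. If an uncertain event of that kind is recorded as Not Related, it drops to the residual row. The coordinating center then hears within 5 business days instead of 24 hours, and the DSMB before its next progress review instead of within 5 business days.

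**The case against.** The strongest reply is that this is a wording inconsistency with limited consequences. The protocol does have a possible level, in 7.3.1 and 7.5, and applying 7.5 at all requires a graded judgment, so sites may record one. The data form is not among the documents, and 2.3 does not cite 7.3.2. On grading, the endpoint's own section names CTCAE v5.0 without exception, so the phrase in 6.2 may be a leftover. Adverse events are collected without an attribution filter until 30 days after treatment, which covers the four-week endpoint window, so no event is lost. Section 9.3 rules out formal hypothesis testing for secondary analyses.

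Most of this stands, and it limits the severity. It does not remove the conflict: a definition that excludes uncertain events and a trigger that includes them cannot both govern the same record, and nothing says which takes precedence.

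A reader might go further and infer that drug-related toxicity will be undercounted. The documents do not support that. Undercounting follows if Related is read literally and every uncertain event is left out. The Not Related definition is equally strict, however, and reading that one literally puts uncertain events among the related and could overcount. The direction of the hematologic modification is also unknown.

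A reader might also extend the point to the toxicity stopping boundary in 9.2. That boundary counts serious toxicities by reference to section 7 and states no attribution condition, so the extension is not supported either.

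**Conclusion.** The point holds as a conflict between stated rules. The drug-related grade 3-5 rate is not reproducible, because its numerator depends on an attribution default that the protocol does not give and on a hematologic grading rule that it does not define. The attribution part alone is worth 3.7 percentage points per uncertain patient at N = 27. The 22-point example rests on assumed counts and shows scale only. The direction of bias is unknown except under the literal reading of Related. Separately, the 7.5 trigger for unexpected, non-serious grade 3-4 events cannot be applied from a two-category record.

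The importance is moderate: no decision rule uses this endpoint and all-cause rates remain recoverable. It is still worth correcting while events are being recorded, because a judgment of possible relation may be hard to reconstruct reliably later. The conclusion assumes that investigators record what 7.3.2 tells them to. If the form already captures the 7.5 levels, the reporting gap closes, but the endpoint still needs a counting rule.

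**What to change.** 1. In 7.3.2, replace the two categories with the scale that 7.5 already uses: unrelated, possible, probable, definite.
2. In 2.3, state that possible or higher counts as drug-related.
3. Reconcile 6.2 and 7.3.2 with 2.3 and 4.2 so that CTCAE v5.0 grades all events. If a hematologic modification was intended, define it and name it as an exception in 2.3.
4. Tabulate all-cause grade 3-5 events beside the drug-related ones. This uses data already collected and does not depend on attribution.

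The cost is wording in three sections and, if the form now offers only two choices, a change to one field. The downside is that the reported drug-related rate may be higher than under a strict count, since some possible events will be due to disease. The all-cause table lets a reader see that.
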